6.4 Study Drug Accountability

Study drug must only be used for subjects enrolled in the trial. The investigational site staff must maintain a careful inventory of study drug. Drugs will be distributed to investigational site staff and patients using FDA guidelines for distribution of investigational agents. Study drug use will be recorded on a Study Drug Inventory Form. This form will contain the following information:

- Subject number and initials for each subject receiving study drug
- Date and quantity of DFMO received by the site
- Date and quantity of DFMO dispensed
- Date and quantity of DFMO returned

At each monitoring visit, the clinical monitor will reconcile with the actual inventory of study drug at each site.

6.5 Concomitant Medications and Treatments

All intercurrent medical conditions will be treated at the discretion of the Investigator according to acceptable community standards of medical care. All concomitant medications and treatments will be documented on the appropriate case report form.

The following medications are not permitted during the trial:

- Any cytotoxic chemotherapy
- Any other investigational treatment
- Any other systemic anti-neoplastic therapy including, but not limited to, immunotherapy, hormonal therapy, targeted therapies, anti-angiogenic therapies, or monoclonal antibody therapy
- Any radiotherapy, including systemically administered radioisotopes, unless administered with palliative intent

Erythropoietin, blood products, anti-emetics, steroids, and transfusions may be administered at the discretion of the Investigator based on established criteria

7.0 STUDY PROCEDURES AND ASSESSMENTS

7.1 Enrollment of Patients

Prior to consent of the subject, the research coordinator at the lead site will be contacted (via e-mail). This coordinator will then reply with study space availability. If the subject fits all enrollment criteria, the site will again contact the coordinator at the lead site for official enrollment confirmation and unique subject identifier assignment. In addition, a study enrollment form will be faxed to the coordinator at the lead site. This determination will be made based on subject data (subject qualifies for study) and current subjects enrolled in trial (i.e. how many subjects are currently enrolled). A subject may NOT be enrolled on trial until official approval from the lead site is received.

All subjects (or patients' legal representatives) must provide written informed consent before any study specific assessments may be performed.

7.2 Screening

The Investigator is responsible for keeping a record of all subjects screened for entry into the study and subsequently excluded.

The following screening procedures must be performed within 14 days prior to the first dose of study drug (7 days extra may be requested from the study chair in exceptional cases). Studies must be done *after* last previous treatment for malignancy:

1. Signed informed consent form. All subjects (or patients' legal representatives) must provide written informed consent before any study specific assessments may be performed. Signed informed consent form for voluntary participation in correlative biologic analysis will also be obtained.
2. CT or MRI to confirm remission status
3. MIBG scan to confirm remission status. Consider PET scan for non MIBG avid subjects.
4. Audiogram
5. Bone marrow aspirate and biopsy
6. Additional Optional Bone Marrow-for subjects with additional informed consent bone marrow samples for biological correlatives per section 12.0)

The following screening procedures must be performed up to 5 days prior to the first dose of study drug.

1. Complete medical and surgical history, including documentation of the histologic evidence of malignancy and prior treatments for cancer. Include all other pertinent medical conditions and a careful history of all prior medical treatments;
2. Demographics;
3. Physical examination (including height and weight), noting all abnormalities including baseline dermatologic and neurologic exam,
4. BSA calculation (from body weight and height);
5. Vital signs, including temperature, pulse rate, and blood pressure
6. ECOG Performance status/Lansky Play status (Appendix I);
7. CBC with differential;
8. Serum electrolytes, blood urea nitrogen (BUN), creatinine, bilirubin, LDH, ALT, AST and ferritin;
9. C-reactive protein (CRP) and Erythrocyte sedimentation rate (ESR)
10. Urine for Vanillylmandelic Acid (VMA) & Homovanillic Acid (HVA)
11. Urine or serum pregnancy test for female subjects of child bearing potential (onset of menses or ≥ 13 years of age);
12. Concomitant medications/therapies including documentation of steroid use and dose;
13. Confirmation of inclusion and exclusion requirements
14. Urine for Biological Correlates per section 12.0

Following completion of all required screening procedures and certification of all inclusion and exclusion criteria by the Investigator, the lead site will be contacted (via e-mail or phone call), at

which time the subject will be enrolled in the trial and a unique subject number assigned. The lead site will act as the central coordinating body. The subject may not start on study until the lead site has provided official approval of enrollment.

7.3 Treatment Phase – Cycle 1

The first cycle will be 28 days in duration. The following procedures must be completed:

Cycle 1 Day 1 (may be performed up to 5 days prior to DFMO administration unless otherwise indicated)

1. Medical History and Physical examination (including body weight), including documentation of an update of all previous abnormalities, any new abnormalities.
2. Vital signs, including temperature, pulse rate, blood pressure (sitting) (to be done on Cycle 1 Day 1);
3. Review and recording of concomitant medications; (to be done on Cycle 1 Day 1)
4. Monitoring and documentation of all AEs and review of concurrent illnesses (to be done on Cycle 1 Day 1)
5. Urine for Biological Correlates per section 12.0 (to be done on Cycle 1 Day 1 in addition to screening sample that was sent in section 7.2)
6. Optional: Blood for Biological Correlates per section 12.0 (additional consent required)
7. Optional: Blood for Biological Correlates (Circulating Tumor Cells to Houston, TX) per section 12.0 (additional consent required).
8. Dispense drug dosing diary

Cycle 1 Day 15 (+/- 3 day window)

Subjects will return to the clinic on Cycle 1 Day 15 for evaluations. The following evaluations will be conducted:

1. History and Physical exam
2. Vital signs, including temperature, pulse rate, and blood pressure (sitting)
3. CBC with differential;
4. Serum electrolytes, BUN, creatinine, bilirubin, ALT, AST; and LDH
5. Review and recording of concomitant medications;
6. Monitoring and documentation of all AEs and review of concurrent illnesses
7. Urine for Biological Correlates per section 12.0
8. Optional: Blood for Biological Correlates per section 12.0 (additional consent required)

7.4 Treatment Phase – Cycles 2-12

All Cycles will be 28 days in duration without interruption. The following procedures must be completed:

Cycle 2-12 Day 1

The following procedures may be performed up to +/- 5 days from Day 1:

1. Medical History and Physical examination (including body weight), including documentation of an update of all previous abnormalities, any new abnormalities.
2. Vital signs, including temperature, pulse rate, blood pressure (sitting);
3. Review and recording of concomitant medications;
4. Monitoring and documentation of all AEs and review of concurrent illnesses
5. BSA calculation (from body weight and height);
6. ECOG Performance status/Lansky Play status (Appendix I);
7. CBC with differential;
8. Serum electrolytes, blood urea nitrogen (BUN), creatinine, bilirubin, LDH, ALT, and AST;
9. C-reactive protein (CRP) and Erythrocyte sedimentation rate (ESR)
10. Urine for Vanillylmandelic Acid (VMA) & Homovanillic Acid (HVA)
11. Urine for Biological Correlates per section 12.0
12. Optional: Blood for Biological Correlates per section 12.0 (additional consent required)
13. Cycles 3, 6, 9, and 12- Optional: Blood for Biological Correlates (Circulating Tumor Cells to Houston, TX) per section 12.0 (additional consent required).
14. Collection of previous cycle drug dosing diary and dispensing of new drug dosing diary
15. Urine or serum pregnancy test for female subjects of child bearing potential (onset of menses or ≥ 13 years of age);

7.5 Treatment Phase – Cycles 13-27

All Cycles will be 28 days in duration without interruption. The following procedures must be completed:

Cycle 13-27 Day 1

The following procedures may be performed up to +/- 5 days from Day 1:

1. Medical History and Physical examination (including body weight), including documentation of an update of all previous abnormalities, any new abnormalities.
2. Vital signs, including temperature, pulse rate, blood pressure (sitting);
3. Review and recording of concomitant medications;
4. Monitoring and documentation of all AEs and review of concurrent illnesses
5. BSA calculation (from body weight and height);

6. ECOG Performance status/Lansky Play status (Appendix I);
7. Urine for Vanillylmandelic Acid (VMA) & Homovanillic Acid (HVA)
8. Urine for Biological Correlates per section 12.0
9. Urine or serum pregnancy test for female subjects of child bearing potential (onset of menses or ≥ 13 years of age);
10. Collection of previous cycle drug dosing diary and dispensing of new drug dosing diary

Additionally at the start of cycles 14*, 17, 21*, 24, and at off therapy (end of cycle 27)

Windows- The following should be done within +/-5 days of the start of specified cycle. For off-therapy/end of cycle 27 they should be done within 30 days (+7) after stopping study drug:

1. CBC with differential;
2. Serum electrolytes, blood urea nitrogen (BUN), creatinine, bilirubin, LDH, ALT, and AST;
3. C-reactive protein (CRP) and Erythrocyte sedimentation rate (ESR)
4. Optional: Blood for Biological Correlates per section 12.0 (additional consent required)
5. Optional: Blood for Biological Correlates (Circulating Tumor Cells to Houston, TX) per section 12.0 (additional consent required).

* Start of cycles 14 and 21 bloodwork stated above can be done at the same time as the IV is placed for the scans done at the end of cycles 13 and 20 in order to reduce the amount of venipuncture the subject experiences.

End of Cycles 3, 6, 9, 13, 20 and off therapy (cycle 27) – scans may be done more often per institutional standards.

Windows- Scans should be done within +/-14 days of the start of next cycle. Off therapy/end of cycle 27 scans should be done within 30 days (+7) after stopping study drug.

1. MIBG scan (for MIBG avid subjects only). Consider PET scan for non MIBG avid subjects.
2. CT/MRI (use same radiologic method as baseline)
3. Bone marrow biopsy and aspirate is to be performed if the treating physician has concerns for progression (If bone marrow testing is being performed and the subject has signed informed consent for the use of tissue in the correlative biologic study as a post-treatment sample please send additional samples per section 12.0)

For patients in first remission who require evaluations for previous front line treatments that are different than the timing of the above schedule, contact the study chair for approval to accept the subjects previously scheduled evaluations instead of repeating the above studies.

End of Cycles 6, 12, and 27

Windows- The following should be done within +/-14 days of the start of the next cycle. For off-therapy/end of cycle 27 it should be done within 30 days (+7) after stopping study drug.

1. Audiogram

(Audiogram should also be done at any time point for any suspected hearing loss)

7.6 PK's for Currently Enrolled Subjects switching to new Formulation DFMO (approximately 10 subjects):

1. **Last Day of Old DFMO Formulation:** Blood for Pharmacokinetic sampling will be done on last day of taking old formulation*. Subject should be instructed to hold their morning dose of old DFMO. Pre-dose PK sample will be collected, and then subject will take old DFMO in clinic. In total, Samples will be collected pre-dose, (Time 0), as well as at 30min, 1 hour, 3 hours, and 6 hours post-dose (exact time should be noted on CRF). Plasma will be separated and frozen at -80°C until analysis per section 12.1.

* Change from old formulation to new formulation may take place on any day of any cycle after subject consents to new formulation and does not need to be on day 1 of a cycle.

2. Start new Formulation of DFMO- Subject should start new formulation at second dose of this day in clinic once all PK's are drawn, this will be Day 1 of new drug formulation.
3. **One day during Days 2-5 of taking on new formulation.** Blood for Pharmacokinetic sampling on one day during days 2-5 of taking the new formulation. Subject should be instructed to hold their morning dose of new DFMO. Pre-dose PK sample will be collected, and then subject will take new DFMO in clinic. In total, Samples will be collected pre-dose, (Time 0), as well as at 30min, 1 hour, 3 hours, and 6 hours post-dose (exact time should be noted on CRF). Plasma will be separated and frozen at -80°C until analysis per section 12.1.

7.7 Other Schedules:

1. Additional imaging or assessments may be done if clinically indicated. Type of imaging, type of assessment and timing should be recorded as well as reason for imaging and/or assessment.
2. Survival will be monitored on an ongoing basis during the study, then every 6 months from the time the subject is off-treatment for a period of 2 years, then yearly for up to five years off therapy.

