4.1 DFMO Treatment

In this study subjects will receive twenty-seven (27) cycles of oral DFMO at a dose of 500 to 1000 mg/m² BID (per dosing chart in section 6.1.2) on each day of a 28 day cycle. DFMO is provided as 250mg tablets.

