12.1 Pharmacokinetic Sample Instructions

Blood samples for the pharmacokinetic assay of DFMO and metabolites will be collected from approximately 10 currently enrolled subjects on their last day of taking the old DFMO formulation and on one day during Days 2-5 of taking the new formulation. Samples will be collected prior to administration of DFMO (Time 0) and at the following times: 30min, 1 hour, 3 hours, and 6 hours post-dose (exact time should be noted on CRF).

The blood samples will be processed to plasma, aliquoted and stored frozen at -80°C until assayed.

PK parameters (C_{max} , T_{max} , AUC_{0-24} , $AUC_{0-\infty}$, $t_{1/2}$, Cl , and Vd) will be determined as appropriate using standard noncompartmental procedures (WINNONLIN software). Individual subject measurements, as well as summary statistics (e.g., mean, standard deviation, range, %CV) will be reported.

Procedures for obtaining, storing and shipping of the pharmacokinetic samples are as follows:

1. One 2cc whole blood specimen will be collected in a purple top tube (EDTA) for each time point.
2. Place samples immediately in ice water bath until ready to process (no longer than 24 hours).
3. Specimen will be spun in a centrifuge at 2,000g for 15 minutes
4. Following centrifugation; using a clean pipette, the plasma from EDTA tube will be aliquoted into a plastic screw capped cryovial.
5. Specimens must be labeled with the participants unique study identifier, PK specific time point (include cycle, day, and time point) and date and time of specimen collection
6. Specimens will then be stored in a -80 freezer until ready to be shipped.

PK Specimen shipping:

- All specimens will be shipped on dry ice following the federal IATA hazardous Specimen Shipping Guidelines
- Specimens should be batch shipped (after each subject completes all PK time points) on a Monday-Thursday.
- PK Specimens will be shipped to the following address:

[name]

Pediatric Oncology Translational Research Laboratory

Coopers Landing

[name]

[name]

Ph: [contact]

[contact]

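### A new-formulation PK profile taken on Day 2 follows a gap of about 18 hours rather than the usual BID gap, so even an identical formulation would look lower on that day

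*Combined protocol and SAP*

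**What the plan says.** Section 7.6 sets out the formulation switch. On the last old-formulation day: "Subject should be instructed to hold their morning dose of old DFMO". The pre-dose sample is taken, the dose is given in clinic, and blood is drawn "as well as at 30min, 1 hour, 3 hours, and 6 hours post-dose". Then: "Subject should start new formulation at second dose of this day in clinic once all PK's are drawn". The switch day itself is counted as the first day on the new product: "this will be Day 1 of new drug formulation".

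The new-formulation profile has the same sampling times and again uses a held morning dose ("Subject should be instructed to hold their morning dose of new DFMO"). Its timing is: "Blood for Pharmacokinetic sampling on one day during days 2-5 of taking the new formulation". Section 12.1 repeats the window: "on one day during Days 2-5 of taking the new formulation". Footnote e of the assessments table also gives Days 2-5.

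The synopsis and section 4.3 are worded a little differently. The synopsis refers to the period after two to five days on the new product, and section 4.3 counts the days from the start of it. Either could be read as excluding the morning after the switch. Sections 7.6 and 12.1 clearly include it.

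Outside the switch day, section 4.1 prescribes "oral DFMO at a dose of 500 to 1000 mg/m² BID", and the table in section 6.1.2 also gives twice-daily dosing. No interval in hours is stated. Section 12.1 plans noncompartmental estimates (Cmax, Tmax, AUC0-24, AUC0-∞, half-life, clearance, volume) with summary statistics, and states no correction for drug remaining from earlier doses.

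**The concern.** Objective 3.2.4 is to evaluate the pharmacokinetics of the new formulation, and the synopsis computes the same parameters for both products, so the patient's old-formulation day serves as the reference. That comparison is clean only if the drug left over from earlier doses is similar at the start of both profiles.

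On Day 2 it is not. The only earlier new-formulation dose was given right after the 6-hour sample on the previous day, about 18 hours before the Day 2 morning dose. The reference profile comes from a patient already on regular twice-daily dosing. The Day 2 profile therefore starts from a lower level and stays lower for reasons unrelated to the product. The bias has one direction, apparent under-exposure on the new formulation, and the planned summaries could not separate it from a real difference. Profiles on Days 3-5 have more regularly spaced doses behind them, so the window mixes two states among about 10 patients.

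**Working it through.** The plan states no bias, precision or power figure for this comparison, so there is none to reproduce. The check asks what the plan would show if the two formulations were identical.

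**Inputs from the documents**
- Sampling at 0, 0.5, 1, 3 and 6 h on both days (section 7.6).
- First new-formulation dose after the 6 h sample on Day 1, taken here as 6 to 6.25 h after the old-formulation dose (section 7.6).
- Day 2 profile the next morning, at 24 h. Gap: 24 − 6 = 18 h.
- Twice-daily dosing otherwise (sections 4.1 and 6.1.2).

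**Assumptions, not in the documents**
- One-compartment linear kinetics, with the same dose and kinetics for both products.
- Half-life 2.5-8 h; absorption rate ka 0.5-2 per hour.
- A 12 h gap before the old-formulation profile (varied below).

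**Formula.** A single dose contributes c(t) = A[exp(−kt) − exp(−ka·t)], with k = ln2/half-life and A = ka/(ka − k). Contributions from all doses are added. AUC0-6 is the linear trapezoid on the plan's times. AUC0-24 is extrapolated as AUC0-6 + C6·[1 − exp(−18λ)]/λ, with λ = ln(C3/C6)/3.

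**Worked case: half-life 5 h, ka 1 per hour, switch dose at 6 h**
- A = 1/(1 − 0.1386) = 1.161.
- Old-day pre-dose level: 1.161 × 0.1895/(1 − 0.1895) = 0.271, where 0.1895 = 2^(−12/5).
- Day 2 pre-dose level: 1.161 × [2^(−18/5) + 2^(−24/5)/(1 − 0.1895)] = 1.161 × (0.0825 + 0.0443) = 0.147, which is 46% lower.

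| Time (h) | 0 | 0.5 | 1 | 3 | 6 |
|---|---|---|---|---|---|
| Old day | 0.271 | 0.632 | 0.820 | 0.887 | 0.621 |
| Day 2 | 0.147 | 0.516 | 0.712 | 0.805 | 0.567 |

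- AUC0-6: 4.558 against 4.047, or −11.2%.
- Cmax at the sampled times: 0.887 against 0.805, or −9.2%.
- Extrapolated AUC0-24: 9.16 against 8.29, or −9.4%.
- Day 3, with 12 h dosing resumed: AUC0-6 4.539, or −0.4%.

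**Range of Day 2 AUC0-6 differences (12 h prior gap, switch dose at 6 h)**

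| Half-life (h) | ka 0.5 | ka 2 |
|---|---|---|
| 2 | −4.9% | −1.7% |
| 2.5 | −7.6% | −3.5% |
| 3 | −10.0% | −5.3% |
| 4 | −13.2% | −8.2% |
| 5 | −14.3% | −9.9% |
| 6 | −14.3% | −10.5% |
| 8 | −12.8% | −10.1% |

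Over half-lives of 2.5-8 h, AUC0-6 is about 3-14% low, Cmax at the sampled times about 3-12% low, and extrapolated AUC0-24 about 3-10% low. At a 2 h half-life AUC0-6 is about 2-5% low. On Day 3, with 12 h gaps, the AUC0-6 bias is at most 1.6% over the same half-lives.

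**Sensitivity to the old-day gap.** Holding the morning dose for a clinic visit may also lengthen the gap before the old-formulation profile. With a 14 h gap and the switch dose at 6.25 h, the Day 2 AUC0-6 deficit is 1.6-7.2%. If the switch dose also slips to 8 h, it is about 1-4%. If the gaps before both profiles were equal at 12 h, it would be zero.

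**Effect on the group mean.** If patients were spread evenly over Days 2-5 (assumption), a quarter would be sampled on Day 2. The mean AUC0-6 would then shift by about 0.25 × 3% to 0.25 × 14%, or 1-3.5%. If all were sampled on Day 2, the full 3-14% would apply.

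**The case against.** The strongest reply is that this matters little. The comparison is a secondary objective in about 10 patients, reported by individual values and summary statistics, with no equivalence margin, test or decision rule. No decision in the documents turns on a few percent. That stands, and it limits the weight of the point.

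Second, the size depends on unstated kinetics and on an assumed 12 h gap, and AUC0-6 is not a planned parameter. This also stands: the range must be quoted with its conditions. But the planned Cmax and AUC0-24 move the same way, and the Day 2 value was lower than the reference in every case above except that of equal gaps.

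Third, the synopsis and section 4.3 can be read as excluding the morning after the switch. Sections 7.6 and 12.1, which a site would follow, allow it, so the difference in wording is a further reason to amend.

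A reader might infer that the whole formulation comparison is biased by up to 14%. The documents do not support that: the figure applies only to Day 2 profiles, and the plan does not say how many there will be. Nor do the documents say that the pre-dose sample serves as a 12-hour trough, so no fault can be built on that use.

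**Conclusion.** The point holds for Day 2 profiles only. The protocol explicitly places the first new-formulation dose after the 6-hour sample and permits a profile the next morning, after a gap of about 18 h that nothing in the plan matches or corrects for.

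The direction is robust as long as the Day 2 gap exceeds the old-day gap. The size is conditional on the assumed kinetics and gaps: about 3-14% for AUC0-6 on Day 2 under the main assumptions, roughly half that with a 14 h old-day gap, and under 2% on Day 3. The effect on the reported mean depends on an uncontrolled mix of sampling days.

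The calculation compares identical products, so it is not evidence that the new formulation under-delivers. The EFS analysis and its error rate are untouched. This is a cheap improvement to a descriptive comparison, not a flaw that invalidates the PK objective.

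**What to change.** - Change the new-formulation PK sampling window to Days 3-5 of the new formulation, counting the switch day as Day 1. Word it identically in the synopsis, footnote e of the assessments table, and sections 4.3, 7.6 and 12.1.
- Record on the CRF the clock times of the doses preceding each profile, old and new. The plan already has a dosing diary for home doses but does not say that it captures clock times.
- Flag any profile already taken on Day 2 and repeat the formulation summary without it.
- Reconcile the switch-day dose spacing in section 7.6 with the BID schedule in sections 4.1 and 6.1.2. That is for the sponsor to resolve; no dosing rule is proposed here.

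Cost: matching text edits in five places, one added CRF item, and one fewer day of scheduling flexibility. No extra visits or blood samples are needed.
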